Table 1 Schedule of Assessments and Procedures

Activity	Screening/Baseline (Day -3 through Day -1) ^a	Treatment Period		Follow-Up	
		Treatment Days up to Last Day of Treatment ^b	Last Day of Treatment (+48 hours)	Day 16 Post Randomization ^{c, d} (±4 days)	Day 28 Post Randomization ^d (±4 days)
Informed consent form	X				
Demographic data	X				
Eligibility criteria	X				
Randomization	X				
Medical history	X				
Physical examination	X	X ^c	X	X	
Vital signs ^e	X	X ^c	X	X	
Chest x-ray ^f	X				
Study-required safety labs ^g	X ^h	X ⁱ	X ^j	X ⁱ	X ⁱ
Review of standard-of-care data: Safety labs ^{g, k} Microbiology assessments ^l Radiological imaging ^m Non-pharmacological treatments ⁿ	X	X	X	X	
Pregnancy test ^o	X	X ^p			
Concomitant medications ^q	X	X	X		
Study drug or comparator administration ^r		X	X		
Pharmacokinetic sampling ^s		X	X		
Adverse event assessment	X	X	X	X	
Serious adverse event assessment	X	X	X	X	X

Activity	Screening/Baseline (Day -3 through Day -1) ^a	Treatment Period		Follow-Up	
		Treatment Days up to Last Day of Treatment ^b	Last Day of Treatment (+48 hours)	Day 16 Post Randomization ^{c, d} (±4 days)	Day 28 Post Randomization ^d (±4 days)
Clinical outcomes and symptom assessments: Early Clinical Response, End of Treatment, and Follow-Up Post Treatment ^t	X	X ^u	X ^v	X ^w	

- a Screening/baseline can occur up to 72 hours prior to randomization. Standard-of-care laboratory data and radiological imaging from up to 72 hours prior to randomization may be used as screening procedures. Screening/baseline and first day of treatment may be the same day.
- b Treatment period is 5 to 7 days for solithromycin and 5 to 10 days for comparators. These assessments and procedures may be done prior to Day 3 if the subject is discharged from the hospital before Day 3.
- c Record vital signs for each day available. Physical examinations should be recorded from baseline and the Day 3 to 4 visit (early clinical outcome assessment) and at the Last Day of Treatment visit.
- d Every effort should be made to bring the subject back. If the subject is unable or unwilling to return, the AEs/SAEs must be collected via telephone/other media.
- e Vital signs taken at the closest time post-drug administration should be noted. If vital signs following drug administration are not available, record the first value of the day.

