7.3 Study Drug Dosage and Administration

Solithromycin will be administered IV or PO according to Table 5 through Table 8 below. If dosing begins with oral therapy, the Day 1 dose will be a loading dose. No loading doses are used with IV solithromycin administration or if switched to oral administration. An IV-to-PO switch can occur after the first IV dose. Subjects starting with oral therapy will receive 5 days of solithromycin treatment, and those starting with IV therapy (regardless of if and when they switch to oral therapy), will receive 7 days of solithromycin treatment.

For subjects receiving the capsule formulation, 200 mg solithromycin capsules will be used to provide the absolute dose of either 200 mg, 400 mg, or 800 mg. The capsule dose will be rounded upwards to the nearest 200 mg, not to exceed an 800 mg loading dose and 400 mg maintenance dose. Study drug should be swallowed with water approximately every 24 hours and at approximately the same time each day (± 4 hours). Study drug can be taken without regard to food.

Table 5 Capsule Dosing Regimens

Age (years)	Weight	Route	Formulation	Day 1 (Max dose: 800 mg)	Days 2 to 5 (Max dose: 400 mg)
6 to 17	>30 kg	PO	Capsules	800 mg	400 mg
	>20 to 30 kg	PO	Capsules	600 mg	400 mg
	≤ 20 kg	PO	Capsules	400 mg	200 mg

Subjects requiring an oral dosage form other than capsules will receive suspension formulation, provided at 275 mg/5 mL strengths, to achieve the age-appropriate mg/mL and solithromycin dose. Any dosing variations within 10% of the calculated suspension dose is not considered a deviation.

Table 6 Suspension Dosing Regimens

Age (years)	Route	Formulation	Day 1 (Max dose: 800 mg)	Days 2 to 5 (Max dose: 400 mg)
12 to 17	PO	Suspension	20 mg/kg (800 mg)	10 mg/kg (400 mg)
6 to <12	PO	Suspension	20 mg/kg	10 mg/kg
2 to <6	PO	Suspension	20 mg/kg	10 mg/kg
2 mo to <2	PO	Suspension	20 mg/kg	10 mg/kg

No loading doses are used with IV solithromycin administration. Intravenous solithromycin should be infused over approximately 60 minutes (± 20 minutes) approximately every 24 hours (± 4 hours). Changes to the infusion duration should be discussed with the study medical monitor prior to study drug administration. Any dosing variations within 10% of the calculated IV dose is not considered a deviation.

Table 7 Intravenous Dosing Regimens

Age (years)	Route	Formulation	Days 1 to 7 (Maximum dose: 400 mg)
12 to 17	IV	Solution	8 mg/kg
6 to <12	IV	Solution	8 mg/kg
2 to <6	IV	Solution	8 mg/kg

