Ampicillin	150-200 mg/kg/day intravenously in equally divided doses every 6 hours	-
Azithromycin	10 mg/kg intravenously/orally on day 1 [500 mg maximum dose] followed by 5 mg/kg orally every 24 hours [250 mg maximum dose]	10 mg/kg orally on day 1 [500 mg maximum dose] followed by 5 mg/kg orally every 24 hours [250 mg maximum dose]
Ceftriaxone	50-75 mg/kg/day intravenously in equally divided doses every 12 hours; total daily dose should not exceed 2 g	50-80 mg/kg intravenously once daily
Erythromycin	40 mg/kg/day orally every 6 hours	30-50 mg/kg/day orally every 6 hours
Erythromycin lactobionate	15 to 20 mg/kg/day intravenously in equally divided doses every 6 hours	50 mg/kg/day intravenously/orally in equally divided doses every 6 hours

Note: if doses of comparator drugs noted in the dosing table above differ those prescribed per standard of care, a site can use the locally prescribed dose.

IV-to-PO switch:

Subjects receiving an IV comparator drug (i.e., ceftriaxone, ampicillin) in any age group may be switched to oral treatment using amoxicillin-clavulanic acid PO (amoxicillin component, 45 mg/kg every 12 hours; subjects weighing ≥40 kg, 875 mg every 12 hours or 500 mg every 8 hours) or amoxicillin alone (45 mg/kg every 12 hours, up to a maximum of 4 g/day).

Subjects must receive 5 to 10 days of treatment with comparator. The exact duration of treatment may be determined at the investigator's discretion.

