10.2 Treatment Period Procedures

10.2.1 Treatment Days up to Last Day of Treatment

1. Every effort should be made to obtain safety labs 72 hours (± 24 hours) after the first dose to include ALT, AST, alkaline phosphatase, total and direct bilirubin, and WBC with

differential. A separate study sample is not required if these labs are obtained at 72 hours (± 24 hours) after the first dose per standard of care.

2. Document physical examination if available per standard of care on the day of clinical outcome assessment only.
3. Document vital signs if available per standard of care on the day of clinical outcome assessment only.
4. Document standard-of-care safety labs as described in Section 10.4.1.
5. Document microbiology assessments as described in Section 10.4.2.
6. Document radiological imaging as described in Section 10.4.3.
7. Document non-pharmacologic treatments on the day of clinical outcome assessment only as described in Section 10.4.3.
8. If the screening visit for females occurred more than 24 hours before receiving the study drug, a pregnancy test will be performed prior to first dose of study drug.
9. Review and record concomitant medications as described in Section 8.3.
10. Administer study drug. If the subject is an outpatient and receiving study drug orally, a dosing diary is included on the capsule blister pack and the label for the suspension. This diary should be completed for each dose taken and brought back to each visit for review and accountability.
11. Obtain PK samples as described in Section 10.4.3.
12. Review and record any AEs and SAEs as described in Section 12.1.
13. Perform clinical outcomes assessment once on days 3–5 (ECR) if the subject is available. A return visit is not required to perform the outcomes assessment.

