12.1 Adverse Events

An AE is any untoward medical occurrence associated with the use of a study drug in humans, whether or not considered drug related. An AE can be a clinical event in the form of signs, symptoms, disease, or laboratory or physiological observations occurring in a human being participating in a clinical study with study drug or comparator, regardless of causal relationship. A “pre-existing” condition is one that is present prior to study drug administration and is reported as part of the subject’s medical history. A pre-existing condition should be reported as an AE only if the frequency, intensity, or character of the pre-existing condition worsens during the course of the study.

Laboratory abnormalities are not considered AEs unless they are associated with clinical signs or symptoms, or require medical intervention. However, a clinically significant laboratory abnormality (e.g. detected on clinical chemistry or hematology) that is independent from the underlying medical condition and that requires medical or surgical intervention, or leads to study drug interruption or discontinuation, will usually be considered an AE.

Lack of efficacy/clinical failure is captured as an efficacy measure and in general will not be considered an AE.

Adverse events will be collected from the time of signing of the informed consent until 28 days post-randomization. In addition, the investigator (or designee) should seek to elicit any clinical or objective reactions by specific questioning (“How have you been feeling?”) and, as appropriate, by examination. Information on all AEs should be recorded on the eCRF. All clearly related signs, symptoms, and results of diagnostic procedures performed because of an AE should be grouped together and recorded as a single diagnosis. The component parts of the diagnosis may be listed for verification. If the AE is a laboratory abnormality that is part of a clinical condition or syndrome, it should be recorded as the syndrome or diagnosis rather than the individual laboratory abnormality.

To avoid vague, ambiguous, or colloquial expressions, all AEs should be recorded in standard medical terminology on the eCRF and on the medical record rather than in the subject’s own words. Each AE will also be described in terms of duration (start and stop date and times), severity, association with the study drug, action(s) taken, and outcome.

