3.1 Study Design

This is a phase 2/3, randomized, open-label, active control, multi-center study to assess the safety and efficacy of solithromycin in adolescents (12 to 17 years inclusive) and children (≥ 2 months to < 12 years of age) with suspected or confirmed Community-acquired Bacterial Pneumonia (CABP).

Subjects who meet all inclusion/exclusion criteria and sign the informed consent/assent will be enrolled. Subjects will be randomized to receive solithromycin or a comparator antibiotic, administered intravenously (IV) or by mouth (PO) in capsules or suspension formulation, with dosing based on a combination of weight and age. The treatment assignment will be open-label. Subjects will be treated for 5 days with oral solithromycin, 7 days with IV or IV-to-oral solithromycin, or for 5 to 10 days with comparator antibiotics (duration of comparator antibiotic per investigator discretion). Subjects will have daily assessments on days of treatment as detailed in the Protocol, and undergo a follow-up visit on last day of therapy (+48 hours). Subjects will be followed for the occurrence of Adverse Events (AEs) for 16 days (± 4 days) after randomization, and Serious Adverse Event (SAE) monitoring will occur up to 28 days (± 4 days) post randomization. PK samples will be collected to assess solithromycin disposition at specified time points. A blinded clinical signs and symptoms assessment will occur at Screening, and clinical outcomes will be assessed by a blinded health care provider at each site on the Day 3 to 4 visit (early clinical response), the Last Day of Treatment Visit (end-of-treatment response), and at the Day 16 Follow-Up visit (16 ± 4 days post-randomization). If the subject is discharged on Day 2 (prior to the Day 3 to 4 visit), the early clinical response assessment will be done on the day of discharge.

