10.2 Primary Safety and Tolerability Endpoints

Primary safety endpoints will be the proportion of subjects in the safety population experiencing a TEAE and the proportion of subjects in the safety population discontinuing study drug due to a related AE. Discontinuation from related AE counts will be created by using any discontinuation from related AE documented in the study drug discontinuation page and the AE data for a subject. The first safety endpoint will be evaluated through the Day 28 visit (28 days ± 4 days after randomization). This will be a composite of TEAEs through Day 16 visit and TESAEs through Day 28 visit. The second safety endpoint will be evaluated through the last day of study drug dosing.

For the primary safety end points, the frequency and percentage of subjects with at least one treatment emergent adverse event, and the frequency and percentage of subjects discontinuing study drug due to a related AE, will be determined. Ninety-five percent Clopper-Pearson (exact) confidence intervals will be calculated for each incidence of occurrence by treatment arm. Summaries will be calculated by treatment arm for the overall safety population, by treatment arm stratified within age group, and within age group and formulation for the solithromycin arm. Patient-level information for adverse events and subjects discontinuing study drug due to a related AE will be listed. For this analysis subjects will be grouped according to their randomized treatment arm assignment (intent-to-treat analysis).

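### Adverse event (AE) enquiry follows treatment length, which differs by arm, so non-serious TEAEs in the first primary endpoint may be found unequally; the direction is not fixed

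*Protocol*

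**What the plan says.** **Treatment length.** Table 1, footnote b, in the Protocol gives the overall ranges: "Treatment period is 5 to 7 days for solithromycin and 5 to 10 days for comparators". Protocol 7.3 is more specific for the oral route: "Subjects starting with oral therapy will receive 5 days of solithromycin treatment". Children who start IV receive 7 days. SAP 3.1 agrees: "Subjects will be treated for 5 days with oral solithromycin, 7 days with IV or IV-to-oral solithromycin, or for 5 to 10 days with comparator". For the comparator, Protocol 7.3 adds: "The exact duration of treatment may be determined at the investigator's discretion". Neither document gives an expected mean comparator duration or an expected split between oral and IV starts.

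**When AEs are asked about.** The AE row of Table 1 marks screening, the treatment days, the last day of treatment (+48 h) and Day 16. Day 28 is for serious events only. SAP 3.1 gives a frequency: "Subjects will have daily assessments on days of treatment as detailed in the Protocol". Protocol 10.2.1 lists the task for the treatment period, "Review and record any AEs and SAEs as described in Section 12.1", without saying how often. Section 12.1 says that the investigator "should seek to elicit any clinical or objective reactions by specific questioning", again without a frequency.

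**What is counted.** SAP 10.2 defines the window of the first primary endpoint, the same in both arms: "This will be a composite of TEAEs through Day 16 visit and TESAEs through Day 28 visit". It is reported as a proportion per arm with a Clopper-Pearson interval. None of the TEAE tables listed in SAP section 12 is restricted to a period in which both arms are scheduled to be on treatment.

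**The concern.** The counting window runs from the calendar, but the intensity of enquiry inside it runs from treatment. After the last-day visit nothing is scheduled until Day 16. An oral-start solithromycin child moves from treatment-day enquiry to a single recalled history after Day 5 (Day 7 at the latest, if the last-day visit uses its full 48 hours). A comparator child on a 10-day course does so after Day 10. A mild rash or loose stools on Day 8 could be picked up by same-day questioning in the second child, but depend on a parent's memory about a week later in the first.

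Protocol 5.3 says that the study is needed to compare safety and tolerability with the comparators, treatment is open-label, and any study team member may make the safety assessments. Readers will set the two TEAE proportions side by side. A difference that comes from the visit schedule could be read as a difference in tolerability.

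**Working it through.** **Reproducing the plan's own figures.** No stated figure concerns how AEs are found. The sample-size tables do reproduce. With 300 subjects and 1% incidence, 1 − 0.99^300 = 0.951 (stated 0.95). One event in 300 has an exact 95% CI of 0.00008 to 0.0184 (stated 0.0001 to 0.018). They show that the sample was set by SAE detection in the solithromycin arm, not by an AE comparison.

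**Is enquiry daily?** SAP 3.1 says so but defers to the Protocol, and Protocol 10.2.1 does not say each day. That section does confine physical examination, vital signs and non-pharmacologic treatments to the outcome-assessment day, and it puts no such limit on AE review. Daily review is therefore the more natural reading, but it is not settled.

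**Size of the artefact.** Inputs:
- d, days of daily enquiry: 5 (oral-start solithromycin), 7 (IV-start), 5 to 10 (comparator). From the documents.
- Window: 16 days. From the documents.
- λ, true event rate per day, equal in both arms: 0.02 or 0.03. Assumed.
- r, the fraction of events after day d that are recalled later: 0.3, 0.5, 0.8. Assumed.

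All events on the d days are taken as captured, so

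P(at least one recorded TEAE) = 1 − exp(−λ[d + (16 − d)r]).

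Example with λ = 0.03 and r = 0.3:
- d = 5: 1 − exp(−0.03 × 8.3) = 22.0%
- d = 10: 1 − exp(−0.03 × 11.8) = 29.8%
- gap: 7.8 points

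Results for λ = 0.03 (recorded TEAE by d, then gaps in points):

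| r | d = 5 | d = 7 | d = 10 | 10 over 5 | 10 over 7 | 7 over 5 |
|---|---|---|---|---|---|---|
| 0.3 | 22.0% | 25.3% | 29.8% | 7.8 | 4.6 | 3.2 |
| 0.5 | 27.0% | 29.2% | 32.3% | 5.3 | 3.1 | 2.2 |
| 0.8 | 33.9% | 34.7% | 35.9% | 2.0 | 1.2 | 0.8 |
| 1.0 | 38.1% | 38.1% | 38.1% | 0 | 0 | 0 |

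At λ = 0.02 the 10-over-5 gap is 1.5 to 5.7 points for r = 0.8 to 0.3.

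**Direction.** The first two gap columns have the comparator recording more events. The last column is IV-start solithromycin against a 5-day comparator course, where solithromycin records 0.8 to 3.2 points more. With equal durations the gap is zero.

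**Mixed durations.** Suppose comparator courses are spread evenly over 5, 6, 7, 8, 9 and 10 days (an assumption). Over λ = 0.02 to 0.03 and r = 0.8 to 0.3, the comparator excess is 0.75 to 3.9 points if all solithromycin children start orally, 0.45 to 2.3 if half do, and 0.15 to 0.7 if all start IV.

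**Crediting the last-day visit.** Treating two further days as fully observed in both arms (7 against 12) leaves gaps of 1.9 to 7.5 points at λ = 0.03, little changed from 2.0 to 7.8.

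**Scale.** At an assumed TEAE proportion of 40%, the 95% half-width of a between-arm difference is 1.96 × √[0.4 × 0.6 × (1/300 + 1/100)] = 11.1 points as planned. SAP section 2 reports fewer than one quarter of 400 enrolled. With an assumed 75 and 25 children the half-width is 22.2 points.

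**The case against.** The strongest reply is that daily questioning rests on one SAP sentence that points back to a Protocol which does not spell it out. Footnote b lets the treatment-period assessments be done before Day 3 on discharge, which suggests one set of assessments around Day 3 to 4. Oral-start outpatients, where the modelled gap is largest, have no explicit daily contact. If review was not daily, both arms have the same nominal AE points: treatment period, last day and Day 16. This stands as a limit on certainty. It does not remove the point, because the timing of the last-day review still follows course length.

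A reader might infer that the schedule biases the endpoint in solithromycin's favour. The documents do not support that as a fixed direction. Comparator length is discretionary from 5 to 10 days, and a 7-day IV-start child can have more treatment-day enquiries than a comparator child. PK sampling, in solithromycin children only, also adds contacts in that arm if enquiry was not otherwise daily, although none after the treatment and last-day visits.

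A reader might also take 2 to 8 points as the expected bias. It is a corner case, with every comparator child on the longest course, every solithromycin child on the shortest, and event and recall rates that the documents do not supply. Day 16 collection is required, by telephone if the child does not return, so only events lost to recall are at issue. Serious events have a common check at Day 28. Finally, extra events caused by longer comparator exposure belong to the regimen being compared and are not an ascertainment error.

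The endpoint is descriptive and its intervals will be wide. That limits the consequence, but imprecision does not correct a systematic difference.

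**Conclusion.** The point holds as a possible difference in ascertainment whose direction is uncertain. AE enquiry follows treatment days and the last-day visit, treatment length differs by arm, the first primary endpoint counts to Day 16 in both, and no planned summary separates the two effects. At 0.03 events per day and recall of 0.3 to 0.8, the artefact is about 2 to 8 points for 5 against 10 days, and below 4 points if comparator courses are spread evenly over 5 to 10 days. It reverses by 0.8 to 3.2 points for 7-day IV-start against 5-day comparator courses, and vanishes with equal durations or full recall. These sizes rest on daily enquiry during treatment, complete capture on those days, a constant and equal event rate in both arms, and the assumed rates. The actual sign can be judged only from the realised durations and route mix.

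**What to change.** In SAP 10.2 and Table 14.4.1, add one supplementary row: the proportion of subjects with a TEAE whose onset is on Days 1-5, by arm with exact 95% CI, beside the through-Day-16 figure. On those days every child in either arm is scheduled to be on assigned drug. Show the distribution of treatment duration by arm with it. SAP section 9 already plans a frequency distribution of days on drug, so this is a matter of placing it beside the endpoint. State also whether AE review was in fact daily on treatment days, since SAP 3.1 and Protocol 10.2.1 do not settle it.

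The cost is one row from onset dates already collected. The row misses late events. It is also clean only if review was daily: otherwise events on Days 1-5 would be recalled at the last-day visit, which comes on Days 5-7 for an oral-start solithromycin child and on Days 10-12 for a 10-day comparator child. It therefore supplements the Day 16 endpoint and does not replace it. Adding AE contacts is no longer possible, because the trial was terminated in March 2018.

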4 LIST OF ABBREVIATIONS AND DEFINITION OF TERMS

AE	adverse event
ALP	alkaline phosphatase
ALT	alanine aminotransferase
AM	alveolar macrophage
AST	aspartate aminotransferase
AUC	area under the concentration versus time curve
AUC ₀₋₂₄	area under the concentration versus time curve at 24 hours
AUC _{tau}	area under the concentration-time curve for the dosing interval
BARDA	Biomedical Advanced Research and Development Authority
bpm	beats per minute
CABP	community-acquired bacterial pneumonia
CA-MRSA	community-acquired methicillin-resistant Staphylococcus aureus
CBC	complete blood count
CE	clinically evaluable
CFR	Code of Federal Regulations (U.S.)
CI	confidence interval
C _{max}	maximum measured plasma concentration
CPK	creatine phosphokinase
CRO	clinical research organization
CRU	clinical research unit
CSF	cerebrospinal fluid
CTCAE	Common Terminology Criteria for Adverse Events
CV	curriculum vitae
DCRI	Duke Clinical Research Institute
DLT	dose-limiting toxicities
DMC	data monitoring committee
DMID	Division of Microbiology and Infectious Diseases
ECG	electrocardiogram
ECR	early clinical response
eCRF	electronic case report form
ELF	epithelial lining fluid
EM	electron microscopy
FDA	Food and Drug Administration (U.S.)
FSH	follicle-stimulating hormone
GC	gonorrhea; gonococcal infection
GCP	Good Clinical Practice
GD	gestational day

GI	gastrointestinal
HCV	hepatitis C virus
HDL	high-density lipoprotein
HDPE	high-density polyethylene
HED	human-equivalent dose
HEENT	head, eyes, ears, nose, throat
hERG	human ether-à-go-go-related gene
HIV	human immunodeficiency virus
IC ₅₀	half-maximal inhibitory concentration
ICF	Informed Consent Form
ICH	International Conference on Harmonization
IEC	Independent Ethics Committee
IND	Investigational New Drug
INR	international normalized ratio
IRB	Institutional Review Board
ITT	intent-to-treat
IUD	intra-uterine device
IV	intravenous
LD	lactation day
LDH	lactate dehydrogenase
LDL	low-density lipoprotein
LLN	lower limit of normal
ME	microbiologically evaluable
MedDRA	Medical Dictionary for Regulatory Activities
MIC	minimum inhibitory concentration
NIH	National Institutes of Health (U.S.)
NOAEL	no-observed-adverse-effect-level
P	parental
PICC	peripherally inserted central catheter
PK	pharmacokinetic
PO	by mouth
PORT	Pneumonia Patient Outcomes Research Team
QD	daily
S. pneumoniae	Streptococcus pneumoniae
SAE	serious adverse event
SAP	Statistical Analysis Plan
SFU	short-term follow-up
TEAE	treatment-emergent adverse event

TOC	test of cure
TQT	Thorough QT/QTc
ULN	upper limit of normal
WBC	white blood cell
WMA	World Medical Association

